10.6.1. Laboratory Values

Laboratory abnormalities will be graded according to the DAIDS grading table Version 2.1, July 2017. Laboratory results are converted to use SI units; only the numeric part of the criteria will be used. If for a laboratory parameter there are multiple grades sharing the same criteria, the maximum grade will be used.

HEMATOLOGY					
	Grade 1	Grade 2	Grade 3	Grade 4	
Absolute Lymphocyte Count, Low (cell/mm³; cells/L) > 5 years of age (not HIV infected)	600 to < 650 0.600 × 10 ⁹ to < 0.650 × 10 ⁹	500 to < 600 0.500 × 10 ⁹ to < 0.600 × 10 ⁹	350 to < 500 0.350 × 10 ⁹ to < 0.500 × 10 ⁹	< 350 < 0.350 × 10 ⁹	
Absolute Neutrophil Count, Low (cells/mm³; cells/L) > 7 days of age	800 to 1,000 0.800 × 10 ⁹ to 1.000 × 10 ⁹	600 to 799 0.600 × 10° to 0.799 × 10°	400 to 599 0.400 × 10 ⁹ to 0.599 × 10 ⁹	< 400 < 0.400 × 10 ⁹	
Hemoglobin, Low (g/dL; mmol/L)	10.0 to 10.9	9.0 to < 10.0	7.0 to < 9.0	< 7.0	
≥ 13 years of age (male only)	6.19 to 6.76	5.57 to < 6.19	4.34 to < 5.57	<4.34	
Hemoglobin, Low (g/dL; mmol/L)	9.5 to 10.4	8.5 to < 9.5	6.5 to < 8.5	< 6.5	
≥ 13 years of age (female only)	5.88 to 6.48	5.25 to < 5.88	4.03 to < 5.25	< 4.03	
Platelets, Decreased (cells/mm³; cells/L)	100,000 to < 125,000 100.000 × 10 ⁹ to < 125.000 × 10 ⁹	50,000 to < 100,000 50.000 × 10 ⁹ to < 100.000 × 10 ⁹	25,000 to < 50,000 25.000 × 10 ⁹ to < 50.000 × 10 ⁹	< 25,000 < 25.000 × 10 ⁹	
White Blood Cell, Decreased (cells/mm³; cells/L) > 7 days of age	2,000 to 2,499 2.000 × 10 ⁹ to 2.499 × 10 ⁹	1,500 to 1,999 1.500 × 10 ⁹ to 1.999 × 10 ⁹	1,000 to 1,499 1.000 × 10 ⁹ to 1.499 × 10 ⁹	< 1,000 < 1.000 × 10 ⁹	

Clinical Chemistry					
	Grade 1	Grade 2	Grade 3	Grade 4	
Albumin, Low (g/dL; g/L)	3.0 to < LLN 30 to < LLN	≥ 2.0 to < 3.0 ≥ 20 to < 30	< 2.0 < 20	NA	
Alkaline Phosphatase, High	1.25 to < 2.5 × ULN	2.5 to < 5.0 × ULN	5.0 to < 10.0 × ULN	≥ 10.0 × ULN	
Alanine Aminotransferase, High	1.25 to < 2.5 × ULN	2.5 to < 5.0 × ULN	5.0 to < 10.0 × ULN	≥ 10.0 ULN	
Amylase (Total), High	1.1 to < 1.5 × ULN	1.5 to < 3.0 × ULN	3.0 to < 5.0 × ULN	≥ 5.0 × ULN	
Aspartate Aminotransferase, High	1.25 to < 2.5 × ULN	2.5 to < 5.0 × ULN	5.0 to < 10.0 × ULN	≥ 10.0 × ULN	
Bicarbonate, Low (mEq/L; mmol/L)	16.0 to < LLN 16.0 to < LLN	11.0 to < 16.0 11.0 to < 16.0	8.0 to < 11.0 8.0 to < 110.	< 8.0 < 8.0	
Direct Bilirubin, High > 28 days of age	NA	NA	> ULN with other signs and symptoms of hepatotoxicity	> ULN with life-threatening consequences (e.g., signs and symptoms of liver failure)	
Total Bilirubin, High > 28 days of age	1.1 to < 1.6 × ULN	1.6 to < 2.6 × ULN	2.6 to < 5.0 × ULN	≥ 5.0 × ULN	
Calcium, High (mg/dL; mmol/L)	10.6 to < 11.5	11.5 to < 12.5	12.5 to < 13.5	≥ 13.5	
≥ 7 days of age	2.65 to < 2.88	2.88 to < 3.13	3.13 to < 3.38	≥ 3.38	
Calcium, Low (mg/dL; mmol/L)	7.8 to < 8.4	7.0 to < 7.8	6.1 to < 7.0	< 6.1	
≥ 7 days of age	1.95 to < 2.10	1.75 to < 1.95	1.53 to < 1.75	< 1.53	
Creatine Kinase, High	3 to < 6 × ULN	6 to < 10 × ULN	10 to < 20 × ULN	≥ 20 × ULN	
Creatinine, High Choose the method that selects for the higher grade	1.1 to 1.3 × ULN	> 1.3 to 1.8 × ULN OR Increase to 1.3 to < 1.5 × participant's baseline	> 1.8 to < 3.5 ULN OR Increase to 1.5 to < 2.0 × participant's baseline	≥ 3.5 × ULN OR Increase of ≥ 2.0 × participant's baseline	
Glucose Fasting, High (mg/dL; mmol/L)	110 to 125 6.11 to < 6.95	> 125 to 250 6.95 to < 13.89	> 250 to 500 13.89 to < 27.75	≥ 500 ≥ 27.75	
Glucose, Low (mg/dL; mmol/L)	55 to 64	40 to < 55	30 to < 40	< 30	
≥ 1 month of age	3.05 to < 3.55	2.22 to < 3.05	1.67 to < 2.22	< 1.67	
Lipase, High	1.1 to < 1.5 × ULN	1.5 to < 3.0 × ULN	3.0 to < 5.0 × ULN	≥ 5.0 × ULN	
Cholesterol, Fasting, High (mg/dL; mmol/L) ≥ 18 years of age	200 to < 240 5.18 to < 6.19	240 to < 300 6.19 to < 7.77	≥ 300 ≥ 7.77	NA	
Triglycerides, Fasting, High (mg/dL;	150 to 300	> 300 to 500	> 500 to < 1.000	> 1,000	
mmol/L)	1.71 to 3.42	> 3.42 to 5.7	> 5.7 to 11.4	> 11.4	
Phosphate, Low (mg/dL; mmol/L)	2.0 to < LLN	1.4 to < 2.0	1.0 to < 1.4	< 1.0	
> 14 years of age	0.65 to < LLN	0.45 to < 0.65	0.32 to < 0.45	< 0.32	

Clinical Chemistry					
	Grade 1	Grade 2	Grade 3	Grade 4	
Detection High (mEg/L, mmg/L)	5.6 to < 6.0	6.0 to < 6.5	6.5 to < 7.0	≥ 7.0	
Potassium, High (mEq/L; mmol/L)	5.6 to < 6.0	6.0 to < 6.5	6.5 to < 7.0	≥ 7.0	
Detection Low (mFa/L mmal/L)	3.0 to < 3.4	2.5 to < 3.0	2.0 to < 2.5	< 2.0	
Potassium, Low (mEq/L; mmol/L)	3.0 to < 3.4	2.5 to < 3.0	2.0 to < 2.5	< 2.0	
Codium High (mFg/L mmgl/L)	146 to < 150	150 to < 154	154 to < 160	≥ 160	
Sodium, High (mEq/L; mmol/L)	146 to < 150	150 to < 154	154 to < 160	≥ 160	
Codium Low (mEa/L: mmol/L)	130 to < 135	125 to < 130	121 to < 125	≤ 120	
Sodium, Low (mEq/L; mmol/L)	130 to < 135	125 to < 130	121 to < 125	≤ 120	
Urio Aoid High (mEg/L: mmol/L)	7.5 to < 10.0	10.0 to < 12.0	12.0 to < 15.0	≥ 15.0	
Uric Acid, High (mEq/L; mmol/L)	0.45 to < 0.59	0.59 to < 0.71	0.71 to < 0.89	≥ 0.89	

NA=not applicable; LLN = lower limit of normal; ULN=upper limit of normal.

Urinalysis					
	Grade 1	Grade 2	Grade 3	Grade 4	
Glucose/Glycosuria (random collection tested by dipstick)	Trace to 1+ or ≤ 250 mg	2+ or > 250 to ≤ 500 mg	> 2+ or > 500 mg	NA	
Protein/Proteinuria (random collection tested by dipstick)	1+	2+	3+ or higher	NA	
Red Blood Cells (RBCs)/Hematuria (not to be reported based on dipstick findings or on blood believed to be of menstrual origin)	6 to < 10 RBCs per high power field	≥ 10 RBCs per high power field	Gross, with or without clots OR with RBC casts OR intervention indicated	Life-threatening consequences	

NA=not applicable

10.7. **Appendix 7: Values of Potential Clinical Importance**

10.7.1. **ECG**

ECG Parameter	Units	Potential Clinically Important Range		
		Lower	Upper	
Absolute				
		< 320[1]	> 450[1]	
Abaaluta OTa Intonual		> 450[2]	≤ 480 ²]	
Absolute QTc Interval	msec	> 480[2]	≤ 500 ^[2]	
		> 500[2]		
Absolute PR Interval	msec	< 120[1]	> 200[1]	
Absolute QRS Interval	msec	< 60[1]	> 120[1]	
Change from Baseline				
	msec	≤ 30 ^[2]		
Increase from Baseline QTc	msec	> 30[1]	≤ 60 ^[2]	
	msec	> 60[2]		

NOTES:

- Represent standard ECG values of potential clinical importance for HV studies.
 Represent further subdivisions of ECG values for analysis.

10.7.2. **Vital Signs**

Vital Sign Parameter	Units	Potential Clinically	Important Range
(Absolute)		Lower	Upper
Systolic Blood Pressure	mmHg	< 85	> 140
Diastolic Blood Pressure	mmHg	< 45	> 90
Heart Rate	bpm	< 40	> 100

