10.9.5. Safety Tables

Safety:	Safety: Tables						
No.	Population	IDSL / Example Shell	Title	Programming Notes	Deliverable		
Advers	e Events (AEs)						
2.1.	Safety	AE1CP	Summary of Adverse Events by System Organ Class and Preferred Term		SAC		
2.2.	Safety	AE1CP	Summary of Drug-Related Adverse Events by System Organ Class and Preferred Term		SAC		
2.3.	Safety	AE3	Summary of Common (>=5%) Adverse Events by Overall Frequency		SAC		
2.4.	Safety	AE15	Summary of Common (>=5%) Non-serious Adverse Events by System Organ Class and Preferred Term (Number of Subjects and Occurrences)		SAC		
2.5.	Safety	AE16	Summary of Serious Adverse Events by System Organ Class and Preferred Term (Number of Subjects and Occurrences)		SAC		
2.6.	Safety	AE5A	Summary of Adverse Events by System Organ Class and Preferred Term and Maximum Intensity		SAC		
Laborat	tory: Chemistry	/					
2.7.	Safety	LB1	Summary of Clinical Chemistry Changes from Baseline		SAC		
2.8.	Safety	LB16	Summary of Clinical Chemistry Results by Maximum Grade Increase Post-Baseline Relative to Baseline		SAC		
Laborat	tory: Hematolo	gy					
2.9.	Safety	LB1	Summary of Hematology Changes from Baseline		SAC		
2.10.	Safety	LB16	Summary of Hematology Results by Maximum Grade Increase Post-Baseline Relative to Baseline		SAC		

Safety:	Tables				
No.	Population	IDSL / Example Shell	Title	Programming Notes	Deliverable
Labora	tory: Urinalysis	S			•
2.11.	Safety	UR3	Summary of Urinalysis Dipstick Results		SAC
2.12.	Safety	LB1	Summary of Urine Concentration Changes from Baseline		SAC
2.13.	Safety	LB16	Summary of Urinalysis by Maximum Grade Increase Post- Baseline Relative to Baseline		SAC
ECG					
2.14.	Safety	EG1	Summary of ECG Findings		SAC
2.15.	Safety	EG2	Summary of ECG Changes from Baseline		SAC
2.16.	Safety	EG10	Summary of Maximum QTc Values Post-Baseline Relative to Baseline by Category		SAC
2.17.	Safety	EG11	Summary of Maximum Increase in QTc Values Post-Baseline Relative to Baseline by Category		SAC
Vital Si	gns				
2.18.	Safety	VS1	Summary of Vital Sign Changes from Baseline		SAC
C-SSR	S				
2.19.	Safety	CSSRS4	Listing of C-SSRS Suicidal Ideation and Behavior Data		SAC

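### The SAP's numeric-only, maximum-grade laboratory rule reports every direct bilirubin above ULN as Grade 4 and can never assign Grade 3; one SI bicarbonate limit also needs checking

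*SAP*

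**What the plan says.** SAP 10.6.1 (Laboratory Values) sets the grading standard and then two programming rules:

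- Units and content: "Laboratory results are converted to use SI units; only the numeric part of the criteria will be used".
- Ties: "If for a laboratory parameter there are multiple grades sharing the same criteria, the maximum grade will be used".

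The chemistry table in the same section has no Grade 1 or 2 for direct bilirubin. Grade 3 is "> ULN with other signs and symptoms of hepatotoxicity". Grade 4 is again a value above ULN, this time qualified by life-threatening consequences such as liver failure. Nothing in the SAP exempts this analyte from the two rules. Direct bilirubin is in the chemistry panel of Protocol Appendix 2.

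The grades are used in Table 2.8, "Summary of Clinical Chemistry Results by Maximum Grade Increase Post-Baseline Relative to Baseline", and in Listings 20 and 21, which show chemistry toxicities and all chemistry data for participants who have one. SAP 5.2 defines a separate laboratory baseline for each period.

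The bicarbonate row gives a mEq/L line followed by a mmol/L line. Its Grade 2 cell reads "11.0 to < 16.0 11.0 to < 16.0", the same in both units. Its Grade 3 cell reads "8.0 to < 11.0 8.0 to < 110", which is not the same in both units.

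**The concern.** For direct bilirubin, the clinical qualifier is the whole difference between Grade 3 and Grade 4. A rule that removes the qualifier and then resolves the tie upwards turns any value above ULN into the most severe grade on the scale. The report could then show Grade 4 chemistry results for participants with a trivial elevation and no clinical finding. Protocol 7.1.4 names Grade 4 laboratory abnormalities among its individual stopping criteria and exempts only asymptomatic cholesterol, triglyceride and CPK increases. A reader of the report would see Grade 4 results with no matching action and could not tell whether the criterion was missed or the grade was an artefact of programming.

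For bicarbonate, the SAP says the SI line is the one applied, so a correct mEq/L line beside it does not rescue a wrong SI limit.

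**Working it through.** **Direct bilirubin.** Inputs: the two rules and the direct bilirubin row of SAP 10.6.1.

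1. Remove the non-numeric text. Grade 3 becomes > ULN and Grade 4 becomes > ULN.
2. The criteria are now identical, so the tie rule applies: max(3, 4) = 4.
3. Test values: 0.9 and 1.0 × ULN receive no grade; 1.01, 1.5 and 3 × ULN each receive Grade 4. No value can receive Grade 3.
4. Effect in Table 2.8, where increase = maximum post-baseline grade − baseline grade:
   - from 1.0 to 1.01 × ULN: 4 − 0 = 4
   - from 1.01 to 3 × ULN: 4 − 4 = 0

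The table therefore shows a four-grade jump for a negligible new crossing and nothing for a threefold rise in a participant already above ULN at that period's baseline. With about 16 participants treated, one new crossing is 1/16 = 6.25% of the cohort. Direct bilirubin is the only row in the printed laboratory tables where two grades reduce to the same numeric criterion.

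**Bicarbonate.** First, a unit check on the row "Bicarbonate, Low (mEq/L; mmol/L"), with ratio = mmol/L limit ÷ mEq/L limit:

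| Limit | mEq/L | mmol/L | Ratio |
|---|---|---|---|
| Grade 1 lower | 16.0 | 16.0 | 1.0 |
| Grade 2 lower | 11.0 | 11.0 | 1.0 |
| Grade 2 upper | 16.0 | 16.0 | 1.0 |
| Grade 3 lower | 8.0 | 8.0 | 1.0 |
| Grade 3 upper | 11.0 | 110 | 10.0 |
| Grade 4 upper | 8.0 | 8.0 | 1.0 |

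Only one limit breaks the pattern, by a factor of ten.

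Next, literal grading on the SI line. The documents give no LLN for bicarbonate, so 18, 20, 22 and 24 mmol/L were assumed in turn. The results below are the same for all four.

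| Value (mmol/L) | Grades met, limit 110 | Grades met, limit 11.0 |
|---|---|---|
| 7 | 4 | 4 |
| 9 | 3 | 3 |
| 12 | 2 and 3 | 2 |
| 17 | 1 and 3 | 1 |
| tested values from LLN to 35 | 3 only | none |

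A fall from 24 to 12 starts at Grade 3 under the printed limit. At 12 the grade is either 3 (change 3 − 3 = 0) or 2 (change 2 − 3 = −1), so no increase appears whichever is chosen. With 11.0 the change is 2 − 0 = 2.

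**The case against.** The best defence of the direct bilirubin rule is that it is a deliberate, prespecified convention. Laboratory data carry no clinical qualifier, and Protocol 8.3 says a more conservative grading scale is preferred. Clinically relevant changes are separately recorded as adverse events and graded by the investigator, safety is only described, and no PK endpoint is touched. This limits the severity. It does not make the output right: "Laboratory abnormalities will be graded according to the DAIDS grading table Version 2.1, July 2017" commits the plan to a scale on which the qualifier is part of the grade, and the rule discards it.

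Three stronger readings are tempting, but the documents do not support them.

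- **That such values are likely because the protocol admits Gilbert's syndrome and some isolated bilirubin elevation.** Exclusion 13 bars Grade 2 to 4 screening abnormalities apart from CPK, lipids and ALT, unless there is a compelling explanation and sponsor assent. The SAP table makes total bilirubin Grade 2 from 1.6 × ULN. The documents give no reference limit for direct bilirubin and no basis for a frequency.
- **That participants would be stopped, or wrongly kept on treatment.** Protocol 7.1.4 concerns decisions made during conduct with the medical monitor, and the liver criterion in 7.1.1 rests on ALT. The SAP grades are for reporting. What remains is a mismatch between report and protocol.
- **That the maximum-grade rule makes bicarbonate Grade 3 override Grades 1 and 2.** That rule covers only grades with the same criteria. These ranges overlap but differ, so the SAP has no rule for values from 11.0 to below LLN.

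The bicarbonate limit is also probably a displaced decimal. The text extracted from the PDF is garbled in nearby rows, and a programmer might notice the figure. In addition, the protocol panel lists carbon dioxide, not bicarbonate, so any effect depends on that analyte being graded on this row.

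**Conclusion.** The direct bilirubin rule is wrong as written. It follows from the SAP's own two sentences and table, needs no misprint and rests on no outside figure. Every value above ULN is Grade 4 and Grade 3 is unreachable. In Table 2.8 only a new crossing of ULN shows, as an increase of four grades; in Listings 20 and 21 any value above ULN shows as Grade 4. Severity is low, since this is the reporting of descriptive safety data in about 16 healthy participants. How many participants would be affected cannot be estimated from the documents.

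The bicarbonate cell is a separate item to verify. If it is printed as 110, and if carbon dioxide is graded on that row, normal values become Grade 3, real falls to 8.0 or above show no grade increase from a normal baseline, and values from 11.0 to below LLN meet two grades.

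**What to change.** 1. Add one sentence to SAP 10.6.1 exempting direct bilirubin from the numeric-only and maximum-grade rules. Values above ULN are flagged and listed without a programmed grade, and Grade 3 or 4 is reported only where the clinical qualifier is documented for that participant. The cost is a small programming change and the loss of an automatic grade for this analyte.
2. Reconcile the grading used for SAP displays with the grading used in conduct under Protocol 7.1.4, and state in the SAP how the two relate, so that a Grade 4 in the report means the same thing in both.
3. Check the SI Grade 3 bicarbonate cell against the source PDF. If it reads 110, correct it to agree with the mEq/L line (8.0 to < 11.0); this also removes the overlap with Grades 1 and 2. State whether carbon dioxide is graded on this row. The cost is one table cell and one line of text.

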10.8. Appendix 8: Abbreviations & Trade Marks

10.8.1. Abbreviations

Abbreviation	Description
ADaM	Analysis Data Model
AE	Adverse Event
AUC	Area under the Plasma Concentration-Time Curve
AUC(0-τ)	AUC from Time 0 to the End of the Dosing Interval at Steady State
CDISC	Clinical Data Interchange Standards Consortium
CI	Confidence Interval
Cmax	Maximum Observed Concentration
C-SSRS	Columbia Suicide Severity Rating Scale
Cτ	Plasma Concentration at the End of the Dosing Interval
CV _b	Coefficient of Variation (Between)
DBF	Database Freeze
DBR	Database Release
DP	Decimal Places
DTG	Dolutegravir
ECG	Electrocardiogram
eCRF	Electronic Case Record Form
GSK	GlaxoSmithKline
HIV	human immunodeficiency virus
ICH	International Conference on Harmonization
IDSL	Integrated Data Standards Library
LLN	Lower Limit of Normal
PK	Pharmacokinetic
QD	Once Daily
RAP	Reporting & Analysis Plan
SAC	Statistical Analysis Complete
SAE Serious Adverse Event	
SD	Standard Deviation
SDTM	Study Data Tabulation Model
Tmax	Time of Maximum Observed Concentration
t1/2	Apparent Terminal Phase Half-Life
ULN	Upper Limit of Normal

10.8.2. Trademarks

Trademarks of the GlaxoSmithKline Group of Companies	
NONE	

	Trademarks not owned by the GlaxoSmithKline Group of Companies
S	AS
٧	VinNonlin

10.9. Appendix 9: List of Data Displays

10.9.1. Data Display Numbering

The following numbering will be applied for RAP generated displays:

Section	Tables	Figures	
Study Population	1.1 to 1.7		
Safety	2.1 to 2.19	2.1	
Pharmacokinetic	3.1 to 3.10	3.1 to 3.10	
Section	Listi	ings	
ICH Listings	1 to 30		
Other Listings	31 to 34		

10.9.2. Mock Example Shell Referencing

Non-IDSL specifications will be referenced as indicated and if required example mock-up displays provided in the Table/Listing/Figure Shells.

Section	Figure	Table	Listing
Study Population	POP_Fn	POP_Tn	POP_Ln
Safety	SAFE_Fn	SAFE_Tn	SAFE_Ln
Pharmacokinetic	PK_Fn	PK_Tn	PK_Ln

NOTES:

Non-Standard displays are indicated in the 'IDSL / Example Shell' or 'Programming Notes' column as '[Non-Standard] + Reference.'

10.9.3. Deliverables

Delivery	Description
SAC	Final Statistical Analysis Complete

10.9.4. Study Population Tables

Study F	Study Population Tables						
No.	Population	IDSL / Example Shell	Title	Programming Notes	Deliverable		
Subjec	t Disposition						
1.1.	Safety	NS1	Summary of Number of Subjects Enrolled by Country and Site ID		SAC		
1.2.	Safety	ES1A	Summary of Subject Disposition for the Subject Conclusion Record		SAC		
1.3.	Screened	SD1	Summary of Screening Status and Reasons for Screen Failures		SAC		
Protoc	ol Deviation						
1.4.	Safety	DV1	Summary of Important Protocol Deviations		SAC		
Demog	raphic and Bas	eline Characteris	tics				
1.5.	Safety	DM3	Summary of Demographic Characteristics		SAC		
1.6.	Safety	DM5	Summary of Race and Racial Combinations		SAC		
1.7.	Safety	DM11	Summary of Age Ranges		SAC		

10.9.5. Safety Tables

Safety:	Safety: Tables						
No.	Population	IDSL / Example Shell	Title	Programming Notes	Deliverable		
Advers	e Events (AEs)						
2.1.	Safety	AE1CP	Summary of Adverse Events by System Organ Class and Preferred Term		SAC		
2.2.	Safety	AE1CP	Summary of Drug-Related Adverse Events by System Organ Class and Preferred Term		SAC		
2.3.	Safety	AE3	Summary of Common (>=5%) Adverse Events by Overall Frequency		SAC		
2.4.	Safety	AE15	Summary of Common (>=5%) Non-serious Adverse Events by System Organ Class and Preferred Term (Number of Subjects and Occurrences)		SAC		
2.5.	Safety	AE16	Summary of Serious Adverse Events by System Organ Class and Preferred Term (Number of Subjects and Occurrences)		SAC		
2.6.	Safety	AE5A	Summary of Adverse Events by System Organ Class and Preferred Term and Maximum Intensity		SAC		
Laborat	tory: Chemistry	/					
2.7.	Safety	LB1	Summary of Clinical Chemistry Changes from Baseline		SAC		
2.8.	Safety	LB16	Summary of Clinical Chemistry Results by Maximum Grade Increase Post-Baseline Relative to Baseline		SAC		
Laborat	tory: Hematolo	gy					
2.9.	Safety	LB1	Summary of Hematology Changes from Baseline		SAC		
2.10.	Safety	LB16	Summary of Hematology Results by Maximum Grade Increase Post-Baseline Relative to Baseline		SAC		

Safety:	Tables				
No.	Population	IDSL / Example Shell	Title	Programming Notes	Deliverable
Labora	tory: Urinalysis	S			•
2.11.	Safety	UR3	Summary of Urinalysis Dipstick Results		SAC
2.12.	Safety	LB1	Summary of Urine Concentration Changes from Baseline		SAC
2.13.	Safety	LB16	Summary of Urinalysis by Maximum Grade Increase Post- Baseline Relative to Baseline		SAC
ECG					
2.14.	Safety	EG1	Summary of ECG Findings		SAC
2.15.	Safety	EG2	Summary of ECG Changes from Baseline		SAC
2.16.	Safety	EG10	Summary of Maximum QTc Values Post-Baseline Relative to Baseline by Category		SAC
2.17.	Safety	EG11	Summary of Maximum Increase in QTc Values Post-Baseline Relative to Baseline by Category		SAC
Vital Si	gns				
2.18.	Safety	VS1	Summary of Vital Sign Changes from Baseline		SAC
C-SSR	S				
2.19.	Safety	CSSRS4	Listing of C-SSRS Suicidal Ideation and Behavior Data		SAC

